4.2 Secondary Outcome Measures

4.2.1 *Physical Function and Activity Secondary Outcome Measures*

All physical function outcome measures are assessed annually over 48 months (see Section 5), unless otherwise specified below.

Short Physical Performance Battery (SPPB) Outcome Measures [1.2.1]:

- Composite SPPB score (composite scoring of repeated chair stand, balance, and gait speed) (*Guralnik et al. J Gerontol. 1994 Mar; 49(2):M85-94.*) For gait speed, faster of the two results (minimum) will be used.
- Physical function deficits defined as a composite SPPB score <10.

Modified Short Physical Performance Battery (mSPPB) Outcome Measures [1.2.1]:

- Composite mSPPB score, modified slightly from Simonsick et al (*J Gerontol A Biol Sci Med Sci* (2001) 56 (10): M644-M649). The composite score (ranging from 0 to 3) defined as a sum of the following 3 components.
 - Chair rise rate (stands/second), as above, divided by maximal possible performance to derive a ratio between 0 to 1 (1 chair stand/second shown by previous studies will be used as the maximal possible performance unless suggested otherwise by the data).
 - Total standing balance time, as the sum of time to hold each of 3 stands (semi-tandem, tandem, and one-leg), divided by 90 (the allotted time of 30 seconds per each stand) to derive a ratio between 0 to 1.

- Gait speed (meters/second) divided by the maximal possible performance to derive a ratio between 0 to 1 (2 meters/second shown by previous studies will be used as the maximal possible performance unless suggested otherwise by the data).
- Balance defined as ability to hold one leg stand for 30 seconds and as a ratio as defined above.
- Gait speed (meters/second) evaluated by time to complete a 4-meter walk. Average of the two results will be used.

Frailty Outcome Measures [1.2.1]:

Assessment of frailty is based on presence of the following criteria: (1) weight loss, (2) exhaustion, (3) low physical activity, (4) slow walk, (5) weak grip strength as described by Fried et al (*J Gerontol A Biol Sci Med Sci*. 2001 Mar;56(3):M146-56.). For gait speed and grip strength, average of the results will be used.

- Frailty classified as non-frail (no criteria present), pre-frail (1 – 2 criteria present), and frail (≥ 3 criteria present).
- Number of frailty components present.
- Presence of each frailty component (weight loss, exhaustion, low physical activity, slow walk, weak grip strength).
- Grip strength (kg) in the dominant hand (average of the results will be used).

Self-Reported Physical Activity and Capacity Outcome Measures [1.3.4]

- Self-reported physical activity via two questions measured on a three-point ordinal scale (usually/often, sometimes, rarely/never) on the Rapid Eating and Activity Assessment for Patients (REAP) assessment. In an average week, how often do you:
 - do less than 30 total minutes of physical activity 3 days a week or more? (Examples: walking briskly, gardening, golf, jogging, swimming, biking, dancing, etc.) [REAP question 26].
 - watch more than 2 hours of television or videos a day? [REAP question 27].
- Self-reported physical capacity measured by the overall score of Duke Activity Status Index (DASI) as described by Hlatky et al. [*Am J Cardiol.* 1989 Sep 15;64(10):651-4.]. Evaluated at REPRIEVE entry and at month 24.

4.2.2 Mechanistic Biomarker Secondary Outcome Measures

Biomarker outcomes are quantified at REPRIEVE entry and at 12 months (see Section 5). They are used in addressing objectives 1.2.2 and 1.3.3 (Section 3).

- Serum concentration of biomarker IL-6.
- Serum concentration of biomarker sTNFR-1.
- Other biomarkers implicated in the pathogenesis of physical function impairment (these may include markers such as sTNFR-2, IP-10, IGF-1, TGF) or those that may mediate the effects of statin treatment on systemic inflammation (CMV IgG).

The specific list of biomarkers of interest may be modified closer to the time of analysis based on the identification of additional biomarkers or pathways involved in this process.

4.2.3 Mechanistic CT Secondary Outcome Measures

CT outcomes for fatty infiltration (muscle density) and muscle mass (area) are quantified at REPRIEVE entry and at 24 months (see Section 5). They are used in addressing objectives 1.2.2, 1.3.2, 1.3.3 and 1.3.6 (Section 3).

- Paraspinal muscle area.
- Trunk and shoulder muscle density (attenuation in HU).
- Trunk and shoulder muscle area.

5 DATA SOURCES FOR OUTCOME MEASURES

The data and samples from the main study REPRIEVE, the mechanistic substudy A5333s and PREPARE will be used as shown in the table below.

Outcome Measure	REPRIEVE (A5332) Entry	Year 1	Year 2	Year 3	Year 4
Physical function battery	A5361s ¹	A5361s ²	A5361s	A5361s	A5361s
Frailty components	A5361s ¹	A5361s ²	A5361s	A5361s	A5361s
Duke Activity Status Index (DASI)	A5332 ³		A5333s/A5361s ⁴		
Self-reported physical activity and sedentary time (REAP) ⁵	A5332 ³	A5361s ²	A5333s/A5361s ⁴	A5361s	A5361s
Myalgia symptom assessment	A5332 ³	A5332 ³	A5332	A5332	A5332
Samples for inflammatory markers	A5332 ³	A5332 ³			
Fasting lipids and insulin sensitivity	A5332/A5333s ³		A5332/A5333s		
CT scan for fatty infiltration and muscle mass of the skeletal trunk muscles	A5333s ³		A5333s		

¹Will be available only to participants who enroll concurrently into REPRIEVE (A5332) and A5361s. For participants who enroll into PREPARE after REPRIEVE entry, evaluation will be conducted at PREPARE entry also.

²Will be available only to participants who enroll into A5361s concurrently or within 12 months of REPRIEVE (A5332) entry. For participants who enroll into PREPARE after REPRIEVE entry, evaluation will be conducted at PREPARE entry also.

³For participants who enroll into A5361s after REPRIEVE (A5332) entry, the data and samples collected in REPRIEVE and A5333s prior to A5361s entry will be used.

⁴For participants not enrolled into A5333s, collected as part of A5361s.

⁵Questions 26 and 27 only.

6 GENERAL ANALYSIS CONSIDERATIONS

6.1 Baseline

Baseline will be defined as the REPRIEVE entry evaluation. The baseline characteristics derived for the main study REPRIEVE will be used, if available. For the physical function and frailty measures, baseline is defined as PREPARE entry evaluation prior to or on the day of the study treatment initiation in REPRIEVE. As such, participants who enroll into PREPARE after initiation of study treatment in REPRIEVE, will not have a baseline (pre-treatment) evaluation.

6.2 Treatment Groups

Treatment groups (placebo vs. pitavastatin) will be defined according to randomization in REPRIEVE. Given the randomization and the double-blinding of treatment, there is no underlying difference expected between treatment groups among the PREPARE participants at baseline. Unless otherwise specified, all of the analyses outlined in this document will be performed by treatment group.

6.3 Time Variables

For derivation of time variables, month is defined as 30 calendar days (as in REPRIEVE) and year as 360 calendar days. Similarly, year will be defined as 360 calendar days in estimation of annual rate of change in an outcome measure.

6.4 Evaluations and Visit Windows

The schedule for visits and evaluations is shown in Section 5. PREPARE post-entry visits (months 12, 24, 36 and 48) are scheduled from REPRIEVE entry, preferably coinciding with the q12 month REPRIEVE visits but within 14 days of REPRIEVE visit is acceptable. The REPRIEVE study protocol specifies a window of ± 21 days for these visits, with a re-scheduling within 7 days of the original visit if the participant is not fasting. For analyses of evaluations by study visits, broader windows of ± 60 days will be used. If multiple evaluations are available within a window, the evaluation closest to the scheduled visit will be used. The study week will be calculated from the REPRIEVE entry date.

6.5 Analysis Population

All eligible randomized participants will be included in the analysis. Participants enrolled and later found ineligible will be evaluated on a case-by-case basis by the study team. Their inclusion or exclusion will be documented in the analysis report.

The analyses of treatment comparisons in the physical function outcome measures will be performed according to the principle of intention-to-treat (ITT), that is, participants will be analyzed according to their randomized treatment assignment regardless of subsequent changes to that treatment or the actual treatment received.

The primary treatment comparisons of biomarker and fatty infiltration outcomes will be as-treated (AT), that is, participants will be analyzed according to their actual treatment received and while on study treatment. Treatment interruptions will be examined and results will be excluded due to treatment interruptions for extended period of time, to be defined.

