10.0 STATISTICAL CONSIDERATIONS

10.1 General Design Issues

A5361s will determine the effects of pitavastatin on physical function and evaluate mechanistic pathways through which pitavastatin affects physical function.

The study will enroll participants from REPRIEVE (A5332) and its mechanistic substudy (A5333s) and follow them for **up to 60** months after entry to REPRIEVE (A5332). Treatment groups (placebo versus pitavastatin) will be defined according to randomization in REPRIEVE (A5332). The primary analyses for all treatment group comparisons will be intent to treat, while supportive secondary analyses as well as analyses examining mechanistic pathways will be as-treated.

While measures of physical function (including both objective and long-term measures of self-assessment) will be assessed as part of A5361s, many of the outcome measures of interest will be available through data collected in REPRIEVE (A5332) and A5333s, as outlined in the Table 10.1-1. If the target recruitment numbers cannot be achieved through A5333s enrollment, the study will open to all participants in REPRIEVE (A5332) enrolled at US ACTG sites. For these participants, only the outcomes measured as part of A5361s or REPRIEVE (A5332) will be available for analysis.

Table 10.1-1: Data Sources for A5361s Outcome Measures

Outcome Measure	REPRIEVE (A5332) Entry	Year 1	Year 2	Year 3	Year 4	Year 5
Physical function battery	A5361s ¹	A5361s ²	A5361s	A5361s	A5361s	A5361s
Frailty components	A5361s ¹	A5361s ²	A5361s	A5361s	A5361s	A5361s
Duke Activity Status Index (DASI)	A5332 ³		A5333s ⁴			A5332⁶
Self-reported physical activity and sedentary time (REAP) ⁵	A5332 ³	A5361s ²	A5333s ⁴	A5361s	A5361s	A5361s
Myalgia symptom assessment	A5332 ³	A5332 ³	A5332	A5332	A5332	A5332
Samples for inflammatory markers	A5332 ³	A5332 ³				
Fasting lipids and insulin sensitivity	A5332/ A5333s ³		A5332/ A5333s			A5332
CT scan for fatty infiltration of the skeletal trunk muscles	A5333s ³		A5333s			

¹ Will be available only to participants who enroll concurrently into REPRIEVE (A5332) and A5361s.

² Will be available only to participants who enroll into A5361s concurrently or within 12 months of REPRIEVE (A5332) entry.

³ For participants who enroll into A5361s after REPRIEVE (A5332) entry, the data and samples collected in REPRIEVE and A5333s prior to A5361s entry will be used.

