10.6.2 Evaluation of the mechanistic pathways through which pitavastatin affects physical function

Distributions of the secondary biomarker outcomes as well as outcomes of fatty muscle infiltration will be described and plotted over time. Pointwise treatment group comparisons will use linear regression adjusted for baseline to provide estimation of the difference in the baseline-adjusted level of the outcomes at each time point. Outcome transformations will be applied as appropriate.

Treatment group comparisons of markers of inflammation and immune activation will be limited to those not described in A5333s. Analyses of fatty infiltration of

muscle will also assess the association of these changes with changes in lipid components and HOMA-IR.

The relationship between markers of inflammation/immune activation, fatty infiltration, and physical function will be assessed via longitudinal modeling of the chair rise rate and expanding each of the appropriate models used to assess treatment group difference including pre- and post-treatment biomarker and fatty infiltration outcomes. The analyses will also examine associations with the following measured covariates/risk factors:

- Demographic and behavioral variables (age, race, sex, menopausal status, BMI, smoking, alcohol use, physical activity by REAP)
- Co-morbid conditions (HBV/HCV, hypertension, diabetes mellitus, chronic kidney disease)
- Use of angiotensin-converting-enzyme inhibitor/angiotensin II receptor blocker (ACE-I/ARB) therapy
- HIV-related variables (CD4 cell count [nadir and current]), HIV RNA, antiretroviral exposure (cumulative and current exposure to ART)
- Muscle symptoms (via the myalgia symptom assessment collected through REPRIEVE [A5332])
- Concomitant medications, specifically, ACE-I/ARB therapy and use of hormonal therapy

Given the assumed temporal associations under study, analyses, including on-treatment measures of biomarkers and fatty muscle infiltration, will only include dependent outcomes assessed from month 24 onward. These analyses will be conducted with and without adjustment for treatment assignment to allow assessment of the degree to which the effects of treatment might be mediated through treatment-associated changes. While further, more formal causal mediation analyses are planned, given the expected statistical developments in the relevant statistical methodology over the next 5 years, these analysis plans will be developed closer to the time of analysis.

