1 INTRODUCTION

This is the primary statistical analysis plan (SAP) for PREPARE (A5361s), a sub-study of REPRIEVE (A5332). It describes the outcome measures and general analytic approaches proposed for the primary statistical analysis, and provides a forum for discussion and ultimate agreement between study team members. The outline of the report contents, tables and figures, specific coding details and data sources will be developed as a separate Analysis Implementation Plan, a supplement to SAP.

This analysis plan may be updated by the study team as new information becomes available outside of the study, and to modify the list of biomarker outcomes of interest closer to the time of analysis. In addition, the plans to evaluate mechanistic pathways through which pitavastatin affects physical function, including causal mediation analyses, will be developed closer to the time of analysis, given the expected developments in the relevant statistical methodology over the next four years.

Note that this is a team-monitored study. The monitoring reports on the study progress, conduct and data collection to the core study team members are outlined in the Study Monitoring Plan and are not part of this document.

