4.1 Primary Outcome Measures

- Physical Function: Chair rise rate quantified annually over 48 months [1.2.1, 1.2.2, 1.3.3, 1.3.5, 1.4.1, 1.4.2, 1.4.3]. Participants are asked to perform 10 chair stands. Chair rise rate will be calculated as the number of chair stands performed divided by the time to perform chair stands. If participant is unable to complete 10 chair rises, 9 seconds will be used for each chair rise not completed (i.e. a total of 90 seconds for those who tried but were unable to complete any).
- Mechanistic Biomarker: Inflammatory Index Score (IIS) calculated as $1/3 \log [IL-6] + 2/3 \log [sTNFR-1]$ at REPRIEVE entry and 12 months. [1.2.2, 1.3.3]
- Mechanistic CT: Paraspinal muscle density (attenuation in Hounsfield units [HU]) at REPRIEVE entry and 24 months. [1.2.2, 1.3.2, 1.3.3, 1.3.6, 1.4.1, 1.4.2]

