6.7 Statistical Significance Level

Statistical comparisons of the primary outcome measures between treatment groups will be performed as two-sided at 5% Type I error.

Given the multiple primary hypotheses and the various secondary outcomes outlined, it is recognized that there is a multiplicity of analyses to be performed, which leads to an increased probability that at least one of the comparisons could be "significant" by chance. Although the overall level of significance for all treatment comparisons will be 5%, we will be conservative in the interpretation of the secondary and supporting analyses, taking into account the degree of significance, and looking for consistency across outcomes.

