9 EFFECT OF PITAVASTATIN ON INFLAMMATION/IMMUNE ACTIVATION AND SKELETAL TRUNK MUSCLE

This section outlines analyses for the outcomes addressing the secondary objectives 1.3.2 and 1.3.6, and for the effect of pitavastatin on mechanistic biomarker outcomes which are not described in A5333s. Refer to Section 4 for the list of outcome measures.

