9.1 Analysis Considerations

The analyses of mechanistic biomarker and fatty infiltration outcomes will be AT, as defined in Section 6.5.

Descriptive statistics (number of observations, mean and standard deviation, median (Q1 – Q3), P10 – P90, minimum – maximum) and graphical presentations over time will be provided.

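### Paraspinal muscle density is a primary outcome, but the SAP plans its treatment comparison only as-treated, with no ITT version and an interruption rule left open; SAP 10.1 also needs reconciling with protocol 10.1 and 10.6.2

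*SAP*

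**What the plan says.** **Status of the outcome.** Protocol 10.2.1.3 and SAP 4.1 both list it as primary; the SAP entry reads "Paraspinal muscle density (attenuation in Hounsfield units [HU]) at REPRIEVE entry and 24 months". SAP 6.7 adds: "Statistical comparisons of the primary outcome measures between treatment groups will be performed as two-sided at 5% Type I error".

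**Analysis set in the SAP.** SAP 6.5: "The primary treatment comparisons of biomarker and fatty infiltration outcomes will be as-treated (AT"). It defines this as analysis by treatment actually received and while on study treatment. SAP 9.1 repeats it: "The analyses of mechanistic biomarker and fatty infiltration outcomes will be AT, as defined in Section 6.5". SAP 9.2 limits post-baseline data to on-treatment results and drops results after extended interruptions. Both 6.5 and 9.2 leave the length of such an interruption open.

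**Rule in the protocol.** Protocol 10.1 says of its primary analyses that those "for all treatment group comparisons will be intent to treat, while supportive secondary analyses as well as analyses examining mechanistic pathways will be as-treated".

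**Pathway analyses.** SAP 10, which carries the mechanistic-pathway title, is declared ITT in 10.1. Its dependent variable is chair rise rate (SAP 10.3), and CT results enter as explanatory variables.

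**The concern.** A comparison of randomised arms keeps the protection of randomisation only if participants are analysed as randomised, whatever happened afterwards. Here the single planned test of a primary outcome keeps or drops results according to treatment status after randomisation. If stopping differs by arm and is related to muscle density, the estimate mixes drug effect with selection.

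The link is plausible in principle. Protocol 2.1 describes myalgia as a major cause of statin discontinuation, and this outcome is a muscle measure. Protocol 2.2 does say that pitavastatin causes fewer muscle complaints than other statins.

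Without an ITT result beside the as-treated one, a reader cannot see directly how much the restriction matters. The open interruption length adds an undecided choice about which results count. SAP 1 says that "specific coding details and data sources will be developed as a separate Analysis Implementation Plan" and ties that plan to no date before unblinding.

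**Working it through.** **1. Is there an ITT comparison of density elsewhere?**
- SAP 6.5 assigns ITT to the physical function outcomes only.
- SAP 9.3 varies the cohort (all A5333s participants, or those also in PREPARE) but not the analysis set.
- SAP 10 is ITT, but density is not its dependent variable.

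So no ITT comparison of density is planned. The same gap would apply to month-12 IIS if it is compared here. Protocol 10.6.2 and SAP 9.3 limit marker comparisons to those not described in A5333s, so it may not be.

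**2. Does as-treated contradict protocol 10.1?** Two readings are open.
- *It does.* Protocol 10.1 makes primary analyses of all treatment group comparisons ITT, and protocol 10.6.2 uses that term for this analysis: "Pointwise treatment group comparisons will use linear regression adjusted for baseline".
- *It does not.* Protocol 10.6.2 sits under the pathway title, protocol 10.1 makes pathway analyses as-treated, and SAP 9 opens "This section outlines analyses for the outcomes addressing the secondary objectives 1.3.2 and 1.3.6".

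**3. SAP 10.1 against the protocol.** SAP 10.1 (ITT) reads against the pathway clause of protocol 10.1 (as-treated). But protocol 10.6.2 builds the pathway models by extending the treatment-comparison models, which for chair rise rate are ITT. The same section speaks of on-treatment measures of biomarkers and muscle fat. The tension is therefore partly internal to the protocol.

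**4. The plan's own power figure.** Inputs from protocol 10.4.2: 300 per arm, 20% loss (so 240), SD 6 HU, difference 1.8 HU, stated power 95%.
- SE = 6 × √(2/240) = 0.548 HU.
- Power at two-sided 5% = Φ(1.8/0.548 − 1.96) = 90.8%.

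The stated 95% is not reproduced on these inputs. It matches with the loss ignored (300 per arm, 95.7%), at one-sided 5% (95.0%), or with an effective SD of about 5.47 after baseline adjustment. That is a separate matter, and nothing below depends on it.

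**5. Possible selection bias.** The documents give no stopping rates, so these inputs are assumed. Let p1 and p0 be the shares excluded in each arm, and g the density gap between kept and excluded participants. I take g as 0.1 to 0.3 SD, which is 0.6 to 1.8 HU. Bias = (p1 − p0) × g.

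| p1 − p0 | Bias (HU) |
|---|---|
| 0 | 0 |
| 0.02 | 0.01 to 0.04 |
| 0.05 | 0.03 to 0.09 |
| 0.10 | 0.06 to 0.18 |

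The largest value is 0.18/1.8 = 10% of the target. With SE 0.548, a bias of 0.18 HU moves the two-sided Type I error from 5% to about 6.2%; 0.09 HU gives 5.3%. A harsher case (20% against 10% excluded, gap 3 HU, or half an SD) gives 0.3 HU and about 8%. Nothing in the documents supports a gap that large. The planned regression adjusts for baseline density, so only the residual gap would count.

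**6. Cost of ITT in power.** Assumed: 240 per arm, SD 6, no benefit in those who stop, no baseline adjustment.

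| Stopped | ITT, all scanned | ITT, half of stoppers scanned | As-treated |
|---|---|---|---|
| 5% | 87.7% (1.71 HU) | 88.5% (1.754 HU, n = 234) | 89.3% (n = 228) |
| 10% | 84.1% (1.62 HU) | 85.9% (1.705 HU, n = 228) | 87.7% (n = 216) |
| 20% | 74.8% (1.44 HU) | 79.1% (1.60 HU, n = 216) | 83.6% (n = 192) |

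These are illustrations only. SAP 9.2 and 9.3 base the primary CT comparison on all A5333s participants with data, and the documents give no number for them.

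**The case against.** The best defence is that as-treated was chosen in advance for outcomes that both documents label mechanistic, and that protocol 10.1 expressly allows it for pathway analyses. This stands to the extent that a reader who infers a plain breach of protocol 10.1 goes further than the text.

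A reader might also infer that SAP 9 and SAP 10 use different density results, so that the two links of the pathway rest on different participants. The documents do not show this. SAP 10.2 is silent on an on-treatment limit, and protocol 10.6.2 refers to on-treatment measures, which could mean either while on drug or simply post-baseline. The point is unclear, not established. Formal mediation planning is also expressly deferred (SAP 1 and 10.3).

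Some checks exist already. SAP 6.5 says interruptions will be examined, and SAP 6.6 examines missing evaluations and drop-out by treatment group. These would reveal differential loss, though they would not show its effect on the density estimate.

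The open interruption length is a declared placeholder in a SAP that may be updated. Nothing suggests that it would be chosen after unblinding or to favour a result, and taken alone it is only missing detail. The assumed inputs also give little bias. What survives is the absence of any comparison by randomised arm for a primary outcome.

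**Conclusion.** The point holds in a limited form. Paraspinal density is a primary outcome with a two-sided 5% test, and its only planned treatment comparison is as-treated, on on-treatment results, with the interruption rule unset. No ITT comparison is planned. SAP 10.1 and protocol 10.1 also point in opposite directions on pathway analyses, with part of the tension inside the protocol itself.

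The documents do not support saying that the result will be materially biased. On assumed differences in exclusion of 0 to 10 percentage points and gaps of 0.6 to 1.8 HU, the bias is 0 to 0.18 HU against a 1.8 HU target, before baseline adjustment. Under double-blinding, treatment received probably equals the randomised arm for most participants, so the main departure from ITT is the on-treatment restriction. Severity is minor to moderate, because a primary outcome is affected and the remedy is cheap.

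**What to change.** 1. In SAP 6.5, 9.1 and 9.2, add a comparison of month-24 paraspinal density by randomised arm, using all available scans regardless of treatment status. Do the same for month-12 IIS if it is compared here.
2. Report it beside the as-treated result and state which is primary, consistently with protocol 10.1: ITT if the comparison is classed as a treatment group comparison.
3. Before unblinding, fix the interruption length used for exclusion and how actual treatment received is assigned.
4. Reconcile SAP 10.1 and 10.2 with protocol 10.1 and 10.6.2, and state whether SAP 10 uses the same density results as SAP 9.

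The cost is SAP wording and one more run of a regression already planned, with no new data. The downside is a somewhat diluted ITT estimate, limited to scans that exist; A5333s rules on scanning after stopping are not in these documents. The as-treated result is kept.
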